3.2.2 Exposure, dose intensity and treatment compliance

Study drug exposure and dosing information will be collected for acalabrutinib-treated subjects.

Intended treatment duration

Intended treatment duration [days] is defined as the number of days a subject is intended to be on treatment.

A subject is expected to receive 20 doses of acalabrutinib, with each dose taken approximately 12 hours apart. One dose is therefore considered a duration of 0.5 days dosing. Therefore, depending on the timing of the subject's first dose, they can adhere to the dosing schedule and receive 20 doses over two time periods:

- Over the course of 10 days (bid, AM and PM), or
- Over the course of 11 days (one on Day 1 (PM), bid on Day 2-10 (AM and PM), one on Day 11 (AM)).

Since doses are approximately 12 hours (0.5 days) apart, the total intended treatment duration in both of the above scenarios is 10 days:

- $0.5 \text{ days} \times 2 \text{ doses} \times 10 \text{ days} = 10 \text{ days}$
- $(0.5 \text{ days} \times 1 \text{ dose}) + (0.5 \text{ days} \times 2 \text{ doses} \times 9 \text{ days}) + (0.5 \text{ days} \times 1 \text{ dose}) = 10 \text{ days}$

Hence,

$$\text{Intended treatment duration (days)} = 10 \text{ days}$$

Actual treatment duration

Actual treatment duration (days) is defined as the total number of days a subject is on treatment. It is calculated as:

$$\text{Actual treatment duration (days)} = \text{Date of last dose} > 0\text{mg} - \text{Date of first dose} + 1$$

Dose reductions or increases are permitted, and the calculation of actual treatment duration makes no adjustment for any dose modifications that may have occurred.

Average daily dose

The average daily dose (mg) is the average dose a subject received on a given day. It is calculated as

$$\text{Average daily dose (mg)} = \text{total dose received (mg)} / \text{Actual treatment duration (days)}$$

Percentage of Intended Dose

Percentage of intended dose (PID) is the percentage of the actual dose delivered relative to the intended dose. PID is calculated as:

$PID = 100\% * d/D$, where:

- d is the total dose received (mg), and
- D is the total dose of the drug that would be delivered, if there were no modifications to dose or schedule: 2000mg

If a subject overdoses, the start and stop date of the overdose and the dose received will be included in the above derivations of actual treatment duration, average daily dose and PID.

3.2.3 Laboratory assessments

Laboratory tests will be performed as specified in the SoA in the CSP.

The baseline laboratory result is defined as the result obtained on the date of randomization (Day 1). If no result was obtained on the date of randomization, the last result prior to the date of randomization will be used.

Visit windows and how to handle multiple records will be described in Section 4.1.

Change or percentage change from baseline in hematology and clinical chemistry variables, as well as CRP, ferritin and ALC will be calculated for each post-baseline assessment recorded in the eCRF.

Laboratory abnormalities will be defined based on laboratory normal ranges (universal normal ranges for central laboratory tests), and absolute values will be classified as low (below range), normal (within range or limits of range), or high (above range).

Laboratory parameters will also be classified using the National Cancer Institute Common Terminology Criteria (CTC) version 5.0 into CTC grades.

The denominator used in laboratory abnormality summaries will include only evaluable subjects (i.e., those who had sufficient data to have the possibility of an abnormality). For example:

- If an abnormality criterion involves a change from baseline, evaluable subjects would have both a baseline and at least 1 post-baseline value recorded
- If an abnormality criterion does not consider changes from baseline to be evaluable, the subject need only have 1 post-baseline value recorded

3.2.4 Physical examinations and chest imaging, electrocardiograms and echocardiograms

Physical examinations and chest imaging, electrocardiograms and echocardiograms will be performed as per SoA and as described in Section 8.1.5 of the CSP.

A 12-lead electrocardiogram (ECG) will be done at screening, Day 10, and as clinically indicated after study entry. All ECGs will be obtained in triplicate. Each ECG will define heart rhythm, P wave duration, PR interval, RR interval, QRS duration, QT interval, QTc and overall evaluation. Baseline is defined, after taking the average of the triplicates, as the averaged triplicate on the date of randomization (Day 1). If no result was obtained on the date of randomization, the latest result prior to the date of randomization is used.

The left ventricular ejection fraction (LVEF) will be reported when echocardiograms (ECHO) are conducted. The LVEF % will also be reported.

Abnormalities recorded at screening or baseline for ECG or ECHO results will be recorded as a concurrent condition. Abnormalities first recorded during the treatment period will be recorded as AEs unless unequivocally related to the disease under study.

3.2.5 Vital signs and arterial blood gases

The vital signs to be collected are blood pressure, respiratory rate, oxygen saturation [SpO₂], pulse, and body temperature, as per the SoA in the CSP.

The oxygen saturation of the blood will be assessed using standard pulse oximetry or by arterial blood gas for those subjects who have an arterial blood gas obtained.

The vital sign and blood oxygen measurements are: systolic BP (mmHg), diastolic BP (mmHg), MAP (mmHg), pulse rate (bpm), respiratory rate (breaths/min), body temperature and oxygen saturation (%). MAP will be calculated as:

$$\text{diastolic BP} + 1/3 (\text{systolic BP} - \text{diastolic BP}).$$

For all vital signs except oxygen saturation, baseline is defined as the result obtained on the date of randomization (Day 1). If no result was obtained on the date of randomization, the last result prior to the date of randomization will be used.

For oxygen saturation, baseline is defined as the result obtained on the date of randomization (Day 1) only.

Vital sign measurements taken at unscheduled visits will not be used in the summaries of vital signs. However, any vital sign measurements taken at unscheduled visits that are regarded as abnormal or clinically significant will be presented as such.

3.2.6 Oxygen treatment, ventilator use and mSOFA score

If a subject requires oxygen supplementation, data will be recorded, including method of oxygen supplementation and maximum daily flow rate. Fraction of inspired oxygen [FiO_2] will be reported or derived.

For subjects using a nasal cannula or simple mask, the maximum daily flow rate will be entered into the OXYGEN or VENTUSE eCRF and FiO_2 will be derived as per the conversion guidelines in Section 8.3. Note that the conversion is different depending on whether the subject is on a mask or nasal cannula. For subjects on high-flow oxygen therapy or using other types of masks, FiO_2 will be entered directly into the OXYGEN eCRF page. If FiO_2 is entered when a simple mask is selected as the method of oxygen, the value entered in the database will be used instead of deriving the value. For subjects on high-flow oxygen therapy or using other types of masks, FiO_2 will be entered directly into the OXYGEN eCRF page. For subjects on mechanical ventilation, FiO_2 will be entered directly into the VENTUSE eCRF page.

Since FiO_2 is only collected on days that oxygen or mechanical ventilation is used, FiO_2 will be imputed for days that no oxygen or mechanical ventilation is reported. If a subject has no oxygen or mechanical ventilation reported on a given day (method of oxygen (MOXDEL) is blank in the OXYGEN form and type of assisted ventilation (ASSVENTT) is blank in the VENTUSE form) then FiO_2 will be imputed as 21%.

If a subject requires mechanical ventilation, data will be recorded regarding whether ventilator weaning was attempted. For subjects on mechanical ventilation the following ventilator settings will be recorded: tidal volume, FiO_2 , peak airway pressure over the last 24 hours, plateau pressure, positive end expiratory pressure, and respiratory rate. Predicted body weight will be recorded assessment of tidal volume. The data will be recorded daily, and the worst value of the day will be entered in the eCRF.

For subjects on mechanical ventilation, an arterial blood gas (pH, oxygen, carbon dioxide, oxygen saturation and bicarbonate), if available, will be recorded daily.

For subjects admitted to ICU, the modification Sequential Organ Failure Assessment (mSOFA) score will be calculated. For each of the following routine assessments, the worst value of the day will be recorded in the eCRF: oxygen saturation by pulse oximetry (SpO_2)/ FiO_2 (mmHg), platelet count, bilirubin, vasopressor use ($\mu\text{g}/\text{kg}/\text{min}$, mmHg), and creatinine (or urine output).

[figure not shown]
For oxygen, mechanical ventilation and mSOFA variables, baseline is defined as the result obtained on the date of randomization (Day 1) only.

3.3 Pharmacokinetic variables

The PK of acalabrutinib and its active metabolite (ACP-5862) in subjects with COVID-19 when administered with BSC is a secondary endpoint. The PK will be assessed by summarizing the plasma concentrations for both analytes at the specified time points. Additionally, PK parameters for acalabrutinib and ACP-5862 (such as, maximum observed concentration (C_{max}) and AUC) may be estimated, as considered appropriate.

Pharmacokinetic concentration data will be collected as per the SoA in the CSP. Plasma concentrations of study drug and/or metabolite are used as supplied by the analytical laboratory for PK analysis.

3.4 Exploratory pharmacodynamic and correlative variables

3.5 Other variables

3.5.1 Baseline characteristics

Baseline characteristics that will be collected or derived are:

- Demographics: Age (years), sex, race and ethnicity
- Subject characteristics: Weight, height and body mass index (BMI), where $BMI (kg/m^2) = Weight/Height^2$
- Medical history: Name of past and/or concomitant diseases (verbatim and coded using the MedDRA dictionary version 23.0), start and stop dates
- Relevant surgical history: Surgical procedure (verbatim and coded using the MedDRA dictionary version 23.0)
- Pregnancy status for applicable subjects only: test date and result (positive or negative)

- History of substance abuse: cigarettes (former/current/never), vaping (former/current/never), recreational inhaled drugs (former/current/never), alcohol (former/current/never)
- SARS-CoV-2 infection comorbidities: infection comorbidities prior to admission, subcategory, comorbidity start and stop date
- SARS-CoV-2 infection risk factors/lifestyle events: infection risk factor, infection risk factor start and stop date
- SARS-CoV-2 infection signs and symptoms: infection signs or symptoms, clinical event start and stop date
- Respiratory failure status at baseline (with vs without), as defined in [Table 1](#), where baseline is defined as the result obtained on the date of randomization (Day 1)
- Intensity of oxygen treatment and mechanical ventilation at baseline: most extreme oxygen treatment or mechanical ventilation, flow rate
- Intensity of oxygen treatment and mechanical ventilation prior to baseline: most extreme oxygen treatment or mechanical ventilation, flow rate, duration of treatment

3.5.2 Prior and concomitant medications and procedures

All therapies (drug and non-drug), including herbal preparations, whether prescribed or over-the-counter, that are used during the study will be recorded on the eCRF. Details include generic and/or brand names of the medications, World Health Organisation Drug Dictionary (WHO-DD) encoding (B3 format), reason for use, route, dose, dosing frequency, and start and end dates. Procedures performed during the study will be recorded on the eCRF and details include the procedure name, WHO-DD encoding (B3 format), reason for the procedure, and start and end dates.

Prior therapies are defined as those taken prior to study treatment with a stop date prior to the first dose of study treatment (acalabrutinib + BSC subjects) or prior to randomization (BSC only subjects). For subjects on acalabrutinib + BSC, concomitant therapies and procedures are defined as those with a stop date on or after the first dose date of study treatment. Start date may be before or after first dose. For subjects on BSC only, concomitant therapies and procedures are defined as those with a stop date on or after randomization. Start date may be before or after randomization.

Best supportive care medication will be collected as a concomitant medication with therapy reason as 'disease under study'.

Missing start and stop dates for medications and procedures will be handled using the rules described in Section 4.1

Medications received prior to or concomitantly will be coded using the WHO Drug Dictionary Anatomical Therapeutic Chemical (ATC) classification codes. Concomitant medications will be summarized for the FAS by ATC classification codes. Subjects with the same concomitant medication/procedure multiple times will be counted once per medication/procedure. A medication/procedure that can be classified into more than one chemical and/or therapeutic subgroup will be presented in each subgroup.

4. ANALYSIS METHODS

4.1 General principles

All statistical analyses will be performed by AZ statistical programming group. Any deviations from the analyses presented in this SAP will be detailed in the clinical study report. All outputs will be produced using SAS® version 9.4 or a later version in accordance with AZ standards.

The below mentioned general principles will be followed throughout the study:

- Demography and baseline characteristics data will be summarised using the FAS.
- All efficacy data will be summarised and analysed using the FAS, unless otherwise specified.
- Safety data will be summarized using the SAF.
- PK data will be summarized using the PKAS.
- CCI [REDACTED]
- Descriptive statistics will be used for all variables, as appropriate.
- Stratification factors age (≥ 65 vs < 65 years) and comorbidities (present vs absent) as recorded at randomization in the IRT system will be used for any summaries or analyses using the FAS that are presented by stratification factor. For summaries or analyses by stratification factor performed using the PPAS, the true stratification results (captured in the eCRF) will be used.
- Continuous variables will be summarised by the number of observations (n), mean, standard deviation (SD), median, minimum and maximum and will be based on non-missing observations. The minimum and maximum will be reported to the same

number of decimal places as the raw data recorded in the database. The mean and median will be reported to one more decimal place than the raw data recorded in the database. The SD will be reported to two more decimal places than the raw data recorded in the database.

- Categorical variables will be summarized by frequency counts and percentages and include the number of subjects with present data and the number of subjects with missing (not present) data. Unless stated otherwise, percentages will be calculated based on the population total for each treatment group. Percentages will be presented to one decimal place.
- For the PK and PD summaries the reported results will be summarized using appropriate significant figures rather than decimal places.
- Baseline is defined as the result obtained on the day of randomization (Day 1). If no result was obtained, the latest result prior to the day of randomization is used. Applies to:
 - Baseline for all laboratory assessments
 - Baseline for vital signs except oxygen saturation (SpO₂)
 - Baseline ECG assessment
- Baseline is defined as the result obtained on the day of randomization (Day 1) only. Applies to:
 - Respiratory failure status at baseline
 - Baseline oxygen saturation (SpO₂)
 - Baseline for all oxygen and mechanical ventilation assessments
 - Baseline ordinal scale score
 - Baseline mSOFA score
- For all summaries, change from baseline variables will be calculated as the post-baseline value minus the value at baseline. The percentage change from baseline will be calculated as $((\text{post-baseline value} - \text{baseline value}) / \text{baseline value}) \times 100$.
- Unless stated otherwise, visit windows will apply as follows:
 - Day 1 (date of randomization): No window unless specified above (where latest result prior to date of randomization can be used)
 - Days 2-10 or discharge (whichever occurs first): no visit window. Note: if a subject is discharged prior to Day 7 they will visit the site for an assessment 2 to 4 days after discharge. Assessments should match those for Day 10.

- Day 14: ± 2 days
- Day 28: ± 3 days
- Arm 1 Safety follow-up at 28 days after last dose of acalabrutinib: ± 3 days
- Arm 2 Safety follow-up (for AEs, concomitant medications and survival assessment) at 38 days after randomization: ± 3 days
- Long-term follow-up 90 days after randomization: ± 7 days
- Observations recorded on the date closest to the scheduled assessment day (as long as this is within the visit window) will be used as the scheduled assessment. If Any observations recorded outside of the visit window will be considered unscheduled visit observations and will not be included in visit-based summaries at a treatment-group level. If multiple observations are recorded per day, or observations within a visit window are equidistant from the target day, the worst assessment reported will be used as the scheduled assessment. For laboratory and vital signs assessments, this is the maximum reported value.
- Visit-based summaries will include: Baseline (Day 1), Day 2-10, Day 14 and Day 28 where applicable, as per SoA.
- For listings at a subject level, all values will be included (regardless of whether they appear in a corresponding visit-based summary) when deriving a patient level statistic such as a maximum.

No imputation of values for missing data will be performed except for missing or partial start and end dates for AEs and concomitant medication(CM) (Table 6). If the data cut-off/snapshot date or the subject’s date of death is prior to the date imputed based on the rules outlined below, then the earliest of these dates will be imputed.

Table 6 Imputation rules for missing or partial AE on concomitant medication dates

Form		Imputation	
		Acalabrutinib + BSC	BSC alone
	Start date		
	Missing		

AE and CM	AE/CM ended before first dose date/ randomization date	Impute 1 st January with year being the same year as CM/AE end date	
	AE/CM ended after first dose date/ randomization date	Impute date of first dose	Impute date of randomization
	Partial		
AE and CM	Missing day	Impute 1 st of the month unless AE/CM start month is the same month as the first dose, then impute date of first dose. Check start date is prior to end date.	Impute 1 st of the month unless AE/CM start month is the same month as randomization, then impute date of randomization. Check start date is prior to end date.
	Missing day and month	Impute 1 st January unless AE/CM start year is the same year as the first dose, then impute date of first dose. Check start date is prior to end date. If end date is now prior to start date, impute 1 st January as the start day and month.	Impute 1 st January unless AE/CM start year is the same year as randomization, then impute date of randomization. Check start date is prior to end date. If end date is now prior to start date, impute 1 st January as the start day and month.
	End date		
	Missing		
AE and CM	CM flag ongoing takes any value (yes, no or missing) and CM start date is prior, on or after first dose date/ randomization AE stop date missing	Impute min (date of death, data cut-off/snapshot date)	
	Partial		
CM	Missing day	Impute the last day of the month unless month is the same as month of last dose, then impute date of last dose.	Impute the last day of the month unless month is the same as month of randomization date + 10 days, then impute randomization date + 10 days.

	Missing day and month	Impute date of last dose + 28 days + 3 days	Impute date of randomization + 38 days + 3 days
--	-----------------------	---	---

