5.1 Inclusion Criteria

Subjects are eligible to be included in the study only if **all** of the criteria below apply.

- 1. Ability to understand the purpose and risks of the study and provide signed and dated informed consent or have a legal representative provide consent and authorization to use protected health information (in accordance with national and local patient privacy regulations).
- 2. Men and women ≥18 years of age at the time of signing the Informed Consent Form (ICF).
- 3. SARS-CoV-2 confirmed per World Health Organization criteria (including positive nucleic acid test of any specimen [eg, respiratory, blood, urine, stool, or other bodily fluid]) within 7 days of randomization.
- 4. COVID-19 pneumonia (documented radiographically) requiring hospitalization and oxygen saturation <94% on room air or requires supplemental oxygen.
- 5. Able to swallow pills.
- 6. Willing to follow contraception guidelines (refer to Appendix F).

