3.1.15 Relative change from baseline in oxygenation index

This is defined as the percentage change from baseline in oxygenation index (SpO_2/FiO_2) to Days 3, 5, 7 and 10. For this endpoint, baseline is defined as the observation on the date of randomization (Day 1) only.

Oxygenation index is calculated as

$$SpO_2 [\%] / FiO_2 [\text{decimal}]$$

It will be calculated for the baseline and each post-baseline assessment using the SpO_2 (oxygen saturation) value and the FiO_2 (fraction of inspired oxygen) value collected or derived on the VS and OXYGEN or VENTUSE eCRF pages, respectively. Details on these variables and visit windows are provided in Section 3.2.6 and Section 4.1, respectively.

3.1.16 Time to clinical improvement of at least 2 points (from randomization) on a 9-point category ordinal scale through Day 28

This is defined as the time (in days) from randomization to the date of first demonstrated clinical improvement of at least 2 points (i.e., a decline of two points) on the following 9-point category ordinal scale through Day 28:

0. * Uninfected, no clinical or virological evidence of infection
1. Ambulatory, no limitation of activities
2. Ambulatory, limitation of activities
3. Hospitalized – mild disease, no oxygen therapy
4. Hospitalized – mild disease, oxygen by mask or nasal prongs
5. Hospitalized – severe disease, non-invasive ventilation or high flow oxygen
6. Hospitalised – severe disease, intubation and mechanical ventilation
7. Hospitalized – severe disease, ventilation and additional organ support, such as pressors, renal replacement therapy, extracorporeal membrane oxygenation
8. Death

*Score of zero on 9-point category ordinal scale will not be evaluated in this study.

This information will be collected in the OSCI pages in the eCRF as per the SoA in the CSP.

Baseline ordinal scale score is defined as the result obtained on the date of randomization (Day 1) only.

If a subject does not have an event (i.e., does not demonstrate clinical improvement of at least 2 points) on or before Day 28 and does not withdraw or become lost to follow up from the study on or prior to Day 28, the data will be censored at Day 28. If a subject does not have an event but withdraws from the study or is lost to follow up on or prior to Day 28, the data will be censored at the last date known that the subject has not demonstrated clinical improvement of at least 2 points up to Day 28.

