3.1.17 Time to SpO₂ > 94% on room air

This is defined as the time (in days) from randomization to the first occurrence that SpO₂ > 94% on room air (i.e. not receiving supplementary oxygen) through Day 28. SpO₂ will be captured on the VS module in the eCRF.

Baseline SpO₂ is defined as the result obtained on the date of randomization (Day 1). Subjects with SpO₂ > 94% on room air at baseline will not be included in any analyses of time to SpO₂ > 94% on room air.

If a subject does not experience an event (i.e., does not have SpO₂ > 94% on room air) on or before Day 28 and does not withdraw or become lost to follow up from the study on or prior to Day 28, the data will be censored at Day 28. If a subject does not have an event but withdraws from the study or is lost to follow up on or prior to Day 28, the data will be censored at the last date known that the subject did not have SpO₂ > 94% up to Day 28.

If a subject does not have an event and dies on or before Day 28, they will be censored at Day 28.

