4.4.4 Vital signs

Summary statistics (n, mean, median, SD, minimum, and maximum) for each of the vital signs and the change from baseline at each scheduled post-baseline assessment will be presented by treatment group.

A by-subject listing of all vital sign parameters will be presented; abnormal vital signs will be flagged.

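### SAP 4.1 defines the worst of repeated readings as the maximum, which for SpO2 selects the best reading

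*SAP*

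**What the plan says.** SAP 4.1 assigns to each visit the observation closest to the scheduled day within the window. For several observations on one day, or observations equally distant from the target day, it says that "the worst assessment reported will be used as the scheduled assessment". The next sentence defines that term: "For laboratory and vital signs assessments, this is the maximum reported value". No parameter is exempted.

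SAP 3.2.5 places SpO2 under this rule: "The vital signs to be collected are blood pressure, respiratory rate, oxygen saturation", followed by pulse and temperature. SAP 3.1.17 records SpO2 on the vital-signs form.

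Two places give the direction of SpO2:
- Protocol 5.1 admits patients with pneumonia "requiring hospitalization and oxygen saturation <94% on room air", or who need supplemental oxygen.
- SAP 3.1.17 defines a favourable event, measured from randomization "to the first occurrence that SpO₂ > 94% on room air".

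Two outputs use by-visit SpO2:
- SAP 4.4.4 gives summary statistics "for each of the vital signs and the change from baseline at each scheduled post-baseline assessment".
- SAP 3.1.15 divides SpO2 by FiO2 to form the oxygenation index, a secondary endpoint, and says: "Details on these variables and visit windows are provided in Section 3.2.6 and Section 4.1, respectively".

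**The concern.** A selection rule should follow from its stated principle. Here the principle is to keep the worst reading, and the instruction is to keep the largest number. The two agree only where high is bad. For SpO2 they point in opposite directions.

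A programmer who follows the literal sentence reports the most favourable SpO2 of the day under a rule described as conservative. One who follows the principle departs from the written SAP, and SAP 4.1 requires departures to be detailed in the study report. At stake is whether the by-visit SpO2 tables, and possibly one secondary efficacy endpoint, mean what a reader of the SAP would take them to mean.

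**Working it through.** The plan states no figure on this point, so there is none to reproduce. The check is a comparison of the passages, then an illustration on assumed readings.

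**1. Direction.** SAP 3.1.17 counts a value above 94% on room air as the good outcome, and protocol 5.1 uses a value below 94% on room air as one route to entry. Lower is therefore worse, and the worst of several readings is the minimum. SAP 4.1 selects the maximum.

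**2. Possible exemptions.** SAP 4.1 treats SpO2 separately for baseline (Day 1 only, with no look-back to an earlier value) but not for repeated readings. Elsewhere the SAP allows for low extremes: the modified SOFA inputs in 3.2.6 use the day's worst value without equating it to a maximum, and the laboratory shift tables in 4.4.3 may run to both the minimum and the maximum. Neither changes the rule for by-visit SpO2.

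**3. When the rule acts.**
- Day 1 and Days 2 to 10: no post-baseline window, so only same-day repeats matter.
- Day 14 (±2) and Day 28 (±3): same-day repeats, and ties such as Days 13 and 15 with nothing on Day 14.
- Oxygenation index (Days 3, 5, 7 and 10): same-day repeats only.

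**4. Size for one subject (assumed inputs).** The documents give neither the number of readings per day nor their spread. With one reading a day the effect is zero. With two independent normal readings, the expected gap between maximum and minimum is 1.128 × SD:
- SD 1.0: 1.128 × 1.0 = 1.13 points
- SD 2.0: 1.128 × 2.0 = 2.26 points

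**5. Size for a by-visit mean.** The difference between the rules is the share of subjects with two readings × 1.128 × SD. The shares are assumed as well.

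| Share with two readings | SD 1.0 | SD 2.0 |
|---|---|---|
| 10% | 0.11 points | 0.23 points |
| 50% | 0.56 points | 1.13 points |

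**6. Oxygenation index, if the rule governs its SpO2 input.** By the formula in SAP 8.3, a nasal cannula at 2 L/min gives FiO2 = (2 × 4) + 20 = 28%. Assume same-day readings of 92% and 94%, a gap inside the range in step 4:
- Maximum: 94 / 0.28 = 335.7
- Minimum: 92 / 0.28 = 328.6
- Ratio: 94 / 92 − 1 = 2.2%, whatever the FiO2

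On average, with no true change, mean SpO2 of 93, SD 1.5 and the same FiO2, one baseline reading and two later readings shift the later SpO2 by half of 1.128 × 1.5, which is 0.85 points, or 0.85 / 93 = 0.9%. A simulation of 1,000,000 draws gives +0.94% with the maximum and −0.88% with the minimum. With two readings on both days, both rules give about 0.0%. The index is therefore distorted only when the number of readings differs between baseline and follow-up.

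**The case against.** The strongest reply is that the rule may seldom act and that low values are not lost. Vital signs are scheduled by day, and a single daily entry leaves nothing to choose between. SAP 3.2.5 adds: "Vital sign measurements taken at unscheduled visits will not be used in the summaries of vital signs". Abnormal vital signs are flagged in the listings (SAP 4.4.4), and abnormal unscheduled readings are still presented. This limits the size of the problem. It does not make the sentence right for SpO2.

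The second reply concerns reach. SAP 3.1.15 refers to Section 4.1 for visit windows only, whereas SAP 3.2.3 refers laboratory tests there for visit windows and for multiple records. The SAP also does not say whether worst is taken on the SpO2 input or on the finished index. That is why the effect on the index is stated conditionally. If the rule does not govern the index, nothing says which repeated SpO2 reading enters it, so clarification is needed either way.

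A reader might infer more than the documents support:
- **Bias towards acalabrutinib.** The rule is the same in both arms. In an open-label study repeats could differ in frequency by arm, but nothing in the documents shows that they do.
- **A wrong direction for absolute lymphocyte count (ALC).** SAP 3.2.3 does bring laboratory repeats under Section 4.1, but the documents do not say which direction is worse for this count. It is a question for the sponsor.
- **Earlier events in time to SpO2 above 94%.** That endpoint is defined by first occurrence, and the SAP does not say that the Section 4.1 rule applies to it.
- **A conflict with protocol 8.1.6**, which uses the screening vital sign closest to randomization. A conflict arises only if several pre-randomization values are all entered for Day 1, which the documents do not establish.

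**Conclusion.** The contradiction holds on the text: as written, SAP 4.1 selects the best SpO2 reading under a rule meant to select the worst. It reaches the by-visit SpO2 summaries for same-day repeats and for ties in the Day 14 and Day 28 windows. It reaches the oxygenation index for same-day repeats only, and only if the rule governs the SpO2 input.

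The point is minor. Those outputs are descriptive, the primary endpoint rests on survival and respiratory support and not on SpO2, and no between-arm bias is shown. The actual size cannot be derived from the documents. The figures above depend on assumed repeat frequency, independence, normality and within-day spread, and they fall to zero with one reading a day. Confidence in the contradiction is high; no claim is made about how often it will change a reported value.

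**What to change.** Amend the sentence in SAP 4.1 so that worst is defined by parameter:
- Use the minimum for SpO2, and state that this applies to the SpO2 input of the oxygenation index in SAP 3.1.15.
- Have the sponsor set and list the direction for each remaining vital sign and each laboratory test, including ALC.
- As a query only: if several pre-randomization vital signs can be entered for Day 1, reconcile SAP 4.1 with protocol 8.1.6, or record the difference in SAP Section 7, which now declares no changes.

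The cost is one sentence and a short table of directions. Choosing between minimum and maximum uses readings already held and needs no new data. Applying protocol 8.1.6 within Day 1 would need the times of readings, and the documents do not show that these are recorded; the SAP amendment history gives limited data collection as the reason for its present baseline definitions.
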